9.1.3 Reporting of Pregnancy

Women who are pregnant or breastfeeding as determined by participant self-report or medical record will not be included in this study. Women who cannot confirm their pregnancy status via self-report or medical record will be excluded.

9.2 Classification of an Adverse Event

9.2.1 Severity of Event

For AEs not included in the protocol defined grading system, the following guidelines will be used to describe severity.

- **Mild** – Events require minimal or no treatment and do not interfere with the participant's daily activities.
- **Moderate** – Events result in a low level of inconvenience or concern with the therapeutic measures. Moderate events may cause some interference with functioning.
- **Severe** – Events interrupt a participant's usual daily activity and may require systemic drug therapy or other treatment. Severe events are usually potentially life-threatening or incapacitating.

9.2.2 Relationship to Study Agent

The clinician's assessment of an AE's relationship to study device is part of the documentation process, but it is not a factor in determining what is or is not reported in the study. If there is any doubt as to whether a clinical observation is an AE, the event should be reported. All AEs must have their relationship to the study device documented.

CONFIDENTIAL

This material is the property of the NYU School of Medicine and Langone Medical Center. Do not disclose or use except as authorized in writing by the study sponsor
Interventional Template Version: 11 January 2019

to study agent assessed. In a clinical trial, the study product must always be suspect. To help assess, the following guidelines are used.

- **Related** – *The AE is known to occur with the study agent, there is a reasonable possibility that the study agent caused the AE, or there is a temporal relationship between the study agent and event. Reasonable possibility means that there is evidence to suggest a causal relationship between the study agent and the AE.*
- **Possibly Related** – *The AE may be related to the device. However, other factors may have contributed to the event (e.g., the participant's clinical condition, other concomitant events). Although an AE may rate only as "possibly related" soon after discovery, it can be flagged as requiring more information and later be upgraded to "probably related" or "definitely related," as appropriate.*
- **Not Related** – *There is not a reasonable possibility that the administration of the study agent caused the event, there is no temporal relationship between the study agent and event onset, or an alternate etiology has been established.*

9.2.3 Expectedness

[name] will be responsible for determining whether an AE is expected or unexpected. An AE will be considered unexpected if the nature, severity, or frequency of the event is not consistent with the risk information previously described for the study agent.

9.3 Time Period and Frequency for Event Assessment and Follow-Up

The occurrence of an AE or SAE may come to the attention of study personnel during study visits or upon review by a study monitor. All AEs including local and systemic reactions not meeting the criteria for SAEs will be captured on the appropriate RF. Information to be collected includes event description, date of onset, clinician's assessment of severity, relationship to study product (assessed only by those with the training and authority to make a diagnosis), and time of resolution/stabilization of the event. All AEs occurring while on study must be documented appropriately regardless of relationship. All AEs will be followed to adequate resolution.

Any medical condition that is present at the time that the participant is screened will be considered as baseline and not reported as an AE. However, if the study participant's condition deteriorates at any time during the study, it will be recorded as an AE. UPs will be recorded in the data collection system throughout the study.

Changes in the severity of an AE will be documented to allow an assessment of the duration of the event at each level of severity to be performed. AEs characterized as intermittent require documentation of onset and duration of each episode.

The PI will record all reportable events with start dates occurring any time after informed consent is obtained until 7 (for non-serious AEs) or 30 days (for SAEs) after the last day of study participation. At each study visit, the investigator will inquire about the occurrence of AE/SAEs since the last visit. Events will be followed for outcome information until resolution or stabilization.

All unresolved adverse events should be followed by the investigator until the events are resolved, the subject is lost to follow-up, or the adverse event is otherwise explained. At the last scheduled visit, the investigator should instruct each subject to report any subsequent event(s) that the subject, or the subject's personal physician, believes might reasonably be related to participation in this study. The investigator should notify the study sponsor of any death or adverse event occurring at any time after a subject has discontinued or terminated study participation that may reasonably be related to this study. The sponsor should also be notified if the investigator should become aware of the development of

CONFIDENTIAL

cancer or of a congenital anomaly in a subsequently conceived offspring of a subject that has participated in this study.

9.4 Reporting Procedures – Notifying the IRB

9.4.1 Adverse Event Reporting

Adverse event rates will be calculated and reviewed at DSMP meetings. Adverse event rates will be reported to the IRB as described previously. Should adverse event rates exceed the normal rates observed in the literature, the study PI will place the study on hold and review the safety of the study.

9.4.2 Serious Adverse Event Reporting

Serious adverse events that are related to the study device or interventions will be reported to the IRB within 24 hours of becoming aware of the occurrence.

9.4.3 Unanticipated Problem Reporting

Incidents or events that meet the OHRP criteria for UPs require the creation and completion of an UP report form. It is the site investigator's responsibility to report UPs to their IRB and to the study sponsor. The UP report will include the following information:

- Protocol identifying information: protocol title and number, PI's name, and the IRB project number;
- A detailed description of the event, incident, experience, or outcome;
- An explanation of the basis for determining that the event, incident, experience, or outcome represents an UP;
- A description of any changes to the protocol or other corrective actions that have been taken or are proposed in response to the UP.

To satisfy the requirement for prompt reporting, UPs will be reported using the following timeline:

- UPs that are SAEs will be reported to the IRB and to the study sponsor within 5 business days of the investigator becoming aware of the event.
- Any other UP will be reported to the IRB and to the study sponsor within 10 business days of the investigator becoming aware of the problem.
- All UPs should be reported to appropriate institutional officials (as required by an institution's written reporting procedures), the supporting agency head (or designee), and OHRP within 10 business days of the IR's receipt of the report of the problem from the investigator.

9.5 Reporting Procedures – Notifying the Study Sponsor

The study clinician will complete a SAE Form within the following timelines:

- All deaths and immediately life-threatening events, whether related or unrelated, will be recorded on the SAE Form and submitted to the study sponsor within 24 hours of site awareness. See Section 1, Key Roles for contact information.
- Other SAEs regardless of relationship will be submitted to the study sponsor within 72 hours of site awareness.

All SAEs will be followed until satisfactory resolution or until the site investigator deems the event to be chronic or the adherence to be stable. Other supporting documentation of the event may be requested by the study sponsor and should be provided as soon as possible.

As a follow-up to the initial report, within the following 48 hours of awareness of the event, the investigator shall provide further information, as applicable, on the unanticipated event or the unanticipated problem in the form of a written narrative. This should include a copy of the completed Unanticipated Problem form,

CONFIDENTIAL

This material is the property of the NYU School of Medicine and Langone Medical Center. Do not disclose or use except as authorized in writing by the study sponsor
Interventional Template Version: 11 January 2019

and any other diagnostic information that will assist the understanding of the event. Significant new information on ongoing unanticipated adverse effects shall be provided promptly to the study sponsor.

The study investigator shall complete an Unanticipated Adverse Device Effect Form and submit to the study sponsor and to the reviewing IRB as soon as possible, but in no event later than 10 working days after the investigator first learns of the effect. The study sponsor contact information is provided in Section 1, Key Roles.

As a follow-up to the initial report, within the following 48 hours of awareness of the event, the investigator shall provide further information, as applicable, on the unanticipated event or the unanticipated problem in the form of a written narrative. This should include a copy of the completed Unanticipated Problem form, and any other diagnostic information that will assist the understanding of the event. Significant new information on ongoing unanticipated adverse effects shall be provided promptly to the study sponsor.

The study sponsor is responsible for conducting an evaluation of an unanticipated adverse device effect and shall report the results of such evaluation to FDA and to all reviewing IRBs and participating investigators within 10 working days after the sponsor first receives notice of the effect. Thereafter the sponsor shall submit such additional reports concerning the effect as FDA requests.

9.6 Study Halting Rules

There are no predetermined stopping rules.

9.7 Safety Oversight

9.7.1 Data Safety Monitoring

It is the responsibility of the Principal Investigator to oversee the data safety monitoring of the study at his/her site. Data safety monitoring meetings will occur with every 10th subject enrolled (beginning when first participant is enrolled) and will include careful assessment of research procedures including protocol adherence, regulatory documentation, enrollment (e.g. rate of enrollment, screen fails, withdrawals), unanticipated problems, and any issues that may arise during the course of research. There are no predefined stopping rules.

Meetings will be documented in data safety monitoring reports (DSMR). An annual DSMR will be submitted to the IRB at the time of continuing review. This data safety monitoring will include careful assessment (e.g. frequency, relatedness, and expectancy) and appropriate reporting of adverse events (e.g. skin tingling, itching, warming, irritation) as noted above. Each tDCS administration will occur in the context of a live video visit through Zoom or Webex. With this real-time supervision of treatment, risk will be systematically monitored and minimized.

9.7.2 Medical Monitoring

[name], MD, Director of the NYU Langone MSCCC, will serve as medical monitor for this study. [name] will be responsible for resolving any clinical matters that may arise, including careful assessment of the number and type of serious adverse events, determining relatedness to the research, and resolution.

9.7.3 Clinical Monitoring

N/A

CONFIDENTIAL

This material is the property of the NYU School of Medicine and Langone Medical Center. Do not disclose or use except as authorized in writing by the study sponsor
Interventional Template Version: 11 January 2019

10 Statistical Considerations

10.1 Statistical and Analytical Plans (SAP)

Study data will be collected through REDCap survey function, and this records will be printed and stored in locked cabinet only accessible to the research staff. While survey data is collected via REDCap, no data will be stored in REDCap. All data will be destroyed from REDCap after it is transferred for storage. The identified data will be shared with the BERD component of the Clinical and Translational Research Institute at Wake Forest School of Medicine for analyses purpose.

10.2 Statistical Hypotheses

We will test the hypotheses that there is an interaction between treatment (active vs. sham) and time on 1) distress (K10 & PANAS-NA) and 2) use (TLFB), with additional outcomes addressing mood/anxiety (BDI, STAI), detailed cannabis use (DFAQ-CU), craving (MCQ-17) and withdrawal (CWS).

If the interaction effect for an outcome is significant, we will conclude there is statistical evidence of overall treatment effect. If the spaghetti plots suggest trends (e.g., linear, quadratic, or piecewise changes) we will treat time as a continuous variable and fit repeated measures regression models along with group and its interaction with continuous time as independent variables.

In supplementary analyses, additional factors or covariates will be included in the models (along with their corresponding interactions with group and time) to examine the potential influence of gender, age, MS disability (PDDS), depressive symptoms (BDI), anxiety (STAI) and CUD severity (CUDIT-R) on responsiveness to active vs. sham treatment.

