This material is the property of the NYU School of Medicine and Langone Medical Center. Do not disclose or use except as authorized in writing by the study sponsor
Interventional Template Version: 11 January 2019

PANAS	Positive and Negative Affect Schedule
PDDS	Patient Determined Disability Scale
PI	Principal Investigator
QA	Quality Assurance
QC	Quality Control
RAVLT	Rey Auditory Visual Learning Test
RRMS	Relapse Remitting Multiple Sclerosis
SAE	Serious Adverse Event/Serious Adverse Experience
SDMT	Symbol Digit Modalities Test
SOP	Standard Operating Procedure
STAI	State-Trait Anxiety Inventory
tDCS	Transcranial Direct Current Stimulation
TLFB	Timeline Followback Method Assessment
US	United States
TMS	Transcranial magnetic stimulation

CONFIDENTIAL

This material is the property of the NYU School of Medicine and Langone Medical Center. Do not disclose or use except as authorized in writing by the study sponsor
Interventional Template Version: 11 January 2019

Protocol Summary

Title	A Telehealth tDCS Approach to Decrease Cannabis Use: Towards Reducing Multiple Sclerosis Disability
Short Title	A Telehealth tDCS Approach to Decrease Cannabis Use in MS
Brief Summary	We will recruit 52 patients with MS, CUD, and elevated distress (K10 score 10-35) in a double-blinded, parallel-arm, sham-controlled trial of a completely at-home intervention. We will test 20x20-minute RS-tDCS (2.0 mA, DLPFC: left anodal) paired with guided mindfulness meditation to decrease distress and cannabis use. Participants will be randomized 2:1 to active vs. sham tDCS.
Phase	Phase 2
Objectives	
- Evaluate the effect of DLPFC tDCS to decrease distress component of cannabis use disorder- Evaluate the effect of DLPFC tDCS to reduce cannabis use- Evaluate if DLPFC tDCS related change in cannabis use is linked to a change in distress
Methodology	2:1 Randomized, Parallel-Arm, Double-Blind, Sham-Controlled Design
Endpoint	
Primary Endpoints:
 
- Decrease in Distress by treatment End- Decrease in Cannabis Use by treatment End 
Secondary Endpoints:
 
-Decrease in Distress through 3-month follow-up-Decrease in Cannabis Use through 3-month follow-up
Study Duration	2 years
Participant Duration	Approximately 4.5 months (4-6 weeks of intervention + follow-ups at 1, 2, and 3 months)
Duration of IP administration	20x20 minutes daily sessions of DLPFC tDCS combined with mindfulness meditation

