Population	N=52 female participants (ages 21-65) with RRMS and CUD
Study Sites	NYU Langone Health [name]
Number of participants	N=52 participants expected to be enrolled at NYU Langone Health
Description of Study Procedure	
tDCS is noninvasive brain stimulation device that modulate brain activity delivering a low-intensity electrical current (2.0 mA) through scalp sponge electrodes. Participants will follow an audio track for guided mindfulness during the stimulation.
 
For Active tDCS, the device is programmed to ramp up to 2.0 mA (for 30 seconds), provide constant current throughout session (19 minutes), and then ramp down (for 30 seconds) at the end.
 
For Sham tDCS the device is programmed to ramp up to 2.0 mA (for 30 seconds) followed by a ramp down (30 seconds), with no current delivery for 18 minutes, and then ramp up (for 30 seconds) and down (for 30 seconds) at the end.

Reference Therapy	

CONFIDENTIAL

This material is the property of the NYU School of Medicine and Langone Medical Center. Do not disclose or use except as authorized in writing by the study sponsor

[figure not shown]
Interventional Template Version: 11 JAN 2019

Key Procedures	Active or sham tDCS with simultaneous mindfulness meditation
Statistical Analysis	Multivariate linear regression will be used to evaluate the outcome of each Aim. The dependent measures will be nested within timepoint (Visit 1, 5, 10, 15, 20), with active/sham as fixed effects.

CONFIDENTIAL

This material is the property of the NYU School of Medicine and Langone Medical Center. Do not disclose or use except as authorized in writing by the study sponsor
Interventional Template Version: 11 January 2019

SCHEMATIC OF STUDY DESIGN

CONFIDENTIAL

This material is the property of the NYU School of Medicine and Langone Medical Center. Do not disclose or use except as authorized in writing by the study sponsor
Interventional Template Version: 11 January 2019

1 Key Roles

[name], Principal Investigator
NYU Langone Health — Neurology
[name]
[contact]
[contact]

[name]
NYU Langone Health — Neurology
[name]
[contact]
[name]

[name]
Wake Forest School of Medicine
[name]
[contact]
[contact]

2 Introduction, Background Information and Scientific Rationale

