4.2 Study Endpoints

4.2.1 Primary Study Endpoints

- Change in distress measured by Kessler Psychological Distress Scale (K10) and Positive and Negative Affect Schedule (PANAS) between baseline and treatment-end.
- Change in cannabis use measured by Timeline Followback Method Assessment (TLFB), Marijuana Craving Questionnaire (MCQ-17), Daily Sessions, Frequency, Age of Onset, and Quantity of Cannabis-Use Inventory (DFAQ-CU) and Cannabis Withdrawal Scale (CWS) between baseline and treatment-end.

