10.4.2 Analysis of the Primary and Secondary Endpoint(s)

The efficacy of RS-tDCS to effect the outcomes of each Aim 1 & 2 will be tested using linear mixed effects models. The dependent measures (K10 score, NA, percent of days of use, CWS, MCQ-17) will be nested within timepoint (Visit 1, 5, 10, 15, 20), with active/sham as fixed effects. This will be done using the Matlab function 'fitlme' with REML estimation predicting change from V1 values following each 5 session RS-tDCS interval (Matlab, R2020a, The MathWorks Inc.).

Given that the purpose of this pilot study is to develop effect sizes for a subsequent R01, we will also derive least-squares means effect sizes of our research strategy on distress, NA, percentage of days of use in 4 intervals [V1-V5; V6-V10; V11-V15; V16-V20]. The number of days that elapsed in each interval will be used as a covariate.

CONFIDENTIAL

This material is the property of the NYU School of Medicine and Langone Medical Center. Do not disclose or use except as authorized in writing by the study sponsor
Interventional Template Version: 11 January 2019

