10.4.4 Adherence and Retention Analyses

Compliance with the interventions will be assessed by summarizing the distributions of numbers and proportions of completed sessions by intervention group. Supportive analyses will evaluate the effects of compliance on results for the primary outcome of change in distress from baseline to end of treatment. Compliance measures will be incorporated into the primary outcome of Aim 1 (distress) analysis models to estimate the effect of compliance on the primary outcome.

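### The only decision rule, a treatment-by-time interaction, does not test the stated primary endpoint of change from baseline to treatment-end, and the list of primary measures differs between sections

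*Combined protocol and SAP*

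**What the plan says.** **Endpoint.** The Protocol Summary gives the first primary endpoint as "Decrease in Distress by treatment End". Section 4.2.1 says "Change in distress measured by Kessler Psychological Distress Scale (K10) and Positive and Negative Affect Schedule (PANAS) between baseline and treatment-end", and for the second endpoint "Change in cannabis use measured by Timeline Followback Method Assessment (TLFB), Marijuana Craving Questionnaire (MCQ-17"), followed by DFAQ-CU and CWS over the same period. Section 10.4.4 refers to "the primary outcome of change in distress from baseline to end of treatment".

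**Decision rule.** Section 10.2 sets treatment-by-time hypotheses and then says: "If the interaction effect for an outcome is significant, we will conclude there is statistical evidence of overall treatment effect". It adds that time will be made continuous (linear, quadratic or piecewise) if the spaghetti plots suggest a trend. No other section says what result supports a conclusion.

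**Model.** Section 10.4.2 says the measures "will be nested within timepoint (Visit 1, 5, 10, 15, 20), with active/sham as fixed effects", in a mixed model "predicting change from V1 values following each 5 session RS-tDCS interval". It names no time term and no interaction. It also plans least-squares effect sizes for four intervals, with no test attached. The Protocol Summary says "Multivariate linear regression will be used to evaluate the outcome of each Aim", with the same fixed effect. Section 10.5 confirms change from V1 as the response, four values per participant, and gives the only alpha: 0.05, one-sided.

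**Measures.**

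| Section | Measures |
|---|---|
| 4.2.1 (primary) | K10, PANAS, TLFB, MCQ-17, DFAQ-CU, CWS |
| 10.2 (lead hypotheses) | K10, PANAS-NA, TLFB; the other three cannabis instruments are called additional, alongside BDI and STAI |
| 10.4.2 (modelled) | K10, NA, percent of days of use, CWS, MCQ-17 |
| 10.4.4 | One primary outcome named: change in distress |

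**The concern.** The endpoint is a between-arm difference at one time. The rule is an omnibus test of whether the arm difference changes over time. They are different questions and can give opposite answers.

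The answer also depends on which model is fitted, and the text allows three:

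- **(a)** arm-by-time on change scores at sessions 5, 10, 15 and 20;
- **(b)** arm-by-time with V1 kept as a response level, which the visit list in 10.4.2 permits;
- **(c)** arm as the only fixed effect, as 10.4.2 literally states, which leaves 10.2 with no interaction to test.

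The form of time is chosen after outcome plots are seen. The one-sided alpha of 10.5 cannot apply to an omnibus F test, which has no direction.

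Section 10.4.2 says the pilot exists to supply effect sizes for a later grant. If its stated conclusion rests on the shape of the response over sessions, it need not describe the treatment-end difference that a later trial would be sized on.

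**Working it through.** **Inputs from 10.5.** Design effect 1 + (5 − 1) × 0.8 = 4.2, and 50 × 4.2 / 5 = 42, split 28:14. The plan's figure reproduces. ICC = 0.8.

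**Assumptions.** The documents give no effect size or SD. I take raw variance 1, compound symmetry, two-sided 0.05 and an arm difference of 0.55 SD at session 20, then vary it from 0.4 to 0.7 SD. The transient profile is the exception, with no difference at session 20.

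**Formulas.** Let k = 1/28 + 1/14 = 0.1071. The within-subject error variance is 1 − 0.8 = 0.2, so 0.2k = 0.0214.

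- Omnibus interaction: noncentral F, noncentrality = (sum of squared centred arm differences) / 0.2k; 3 and 120 df for (a), 4 and 160 df for (b).
- Linear trend, if the plots trigger it: 1-df group-by-time on the orthonormal linear contrast; 124 df (a), 166 df (b).
- Reading (c): mean of four change scores, variance 0.2 + 0.2/4 = 0.25, t on 40 df.
- Treatment-end contrast: variance 2 × 0.2 = 0.4, t on 40 df; baseline-adjusted 1 − 0.8² = 0.36, t on 39 df.

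**Worked cases.**

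- Steady 0.55 from session 5, reading (a): all four differences are equal, the centred sum of squares is 0, and power equals alpha at any effect size. Reading (b): differences 0, 0.55 × 4, mean 0.44; sum of squares 0.44² + 4 × 0.11² = 0.242; noncentrality 11.29; power 76%.
- Linear ramp: sum of squares 0.0945 (a) or 0.1891 (b); noncentrality 4.41 or 8.82; power 38% or 64%.
- Transient (0.25, 0.5, 0.25, 0 SD): sum of squares 0.125 or 0.175; noncentrality 5.83 or 8.17; positive in 49% or 60%.
- Contrast: 0.55 / √(0.4 × 0.1071) = 2.66, power 74%. Adjusted: 0.55 / √(0.36 × 0.1071) = 2.80, power 78% by formula, 77% simulated.

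**Chance of a positive result.**

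| Profile | Omnibus (a) | Omnibus (b) | Trend (a) | Trend (b) | (c) | Adjusted contrast |
|---|---|---|---|---|---|---|
| Steady from session 5 | 5% | 76% | 5% | 62–66% | 91% | 77% |
| Linear ramp | 38% | 64% | 55% | 84% | 54% | 77% |
| Delayed (0, half, full, full) | 73% | 86% | 82–83% | 94% | 54% | 77% |
| Transient, none at session 20 | 49% | 60% | 30–33% | 4–5% | 32% | 5% |

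Simulation with 40,000 trials per profile agrees within about 1 point, except for the trend tests, where the ranges shown span formula and simulation.

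**Range, 0.4 to 0.7 SD.** Adjusted contrast 51–94%. Ramp omnibus 21–58% (a), 36–86% (b). Ramp trend 33–76% (a), 57–96% (b). Delayed omnibus 44–92% (a), 56–98% (b).

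**Choosing the time form from plots.** If the smallest p-value of the omnibus, linear and quadratic tests could be used, simulated type I error is 9.3% (a) or 9.8% (b). With omnibus or linear only it is 8.1% or 8.4%. These are ceilings for those choices: the true figure lies between 5% and the ceiling, and piecewise forms are not included.

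**The case against.** A treatment-by-time test is conventional, and total blindness to a steady benefit holds only on reading (a). That is right, but 10.4.2 and 10.5 both describe change from V1 as the response, and even reading (b) does not isolate treatment-end.

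Sections 2.1 and 2.2.2 anticipate effects after sustained treatment. The delayed profile is closest to that, and there the interaction is about equal to or more powerful than the contrast. This stands: no loss of power is shown for the expected course. The steady and transient profiles show what the rule can do, not what the documents predict.

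K10 covers the past four weeks (8.2.1) and treatment lasts four to six weeks, so its windows overlap. If answers average over the window, a steady benefit would look more like a ramp, and power on (a) would be 38% or 32% (omnibus) or 55% or 43% (trend) instead of 5%. This softens the steady case for K10. It does not reach TLFB or remove the mismatch.

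The continuous-time models may be meant only as description, in which case the type I error ceiling does not arise. The Protocol Summary's regression may be a loose name for the same model, and 10.4.2 covers secondary endpoints too, so its five measures need not be a primary list. These are fair readings; the plan should state them. The conflict between 4.2.1 and 10.2 remains either way, as does the absence of DFAQ-CU from the model list.

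At the plan's one-sided 0.05 the contrast has 83% power unadjusted and 87% adjusted, so the two-sided contrast figures above are lower than the plan's own alpha would give.

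**Conclusion.** The concern holds and should be fixed. The mismatch follows from the text and needs no assumed effect size: no section attaches a test or a decision to the treatment-end difference. On change scores the stated rule cannot see a benefit held from session 5. On either interaction reading it can be positive with no difference at session 20.

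The size of the consequence rests on the assumed 0.55 SD, compound symmetry and the chosen profiles. Under a linear build-up alone, the chance of a positive conclusion runs from 38% to 84% according to the model reading and time form, against about 77% for the adjusted treatment-end contrast. The problem is an undefined and mismatched primary test, not a test that is always weaker. The inconsistent list of primary measures is a plain conflict between sections.

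**What to change.** - Name the same single primary variable per aim in 4.2.1, 10.2 and 10.4.2, for example K10 for distress and TLFB percent of days for use.
- Make the primary test the baseline-adjusted active-minus-sham difference at treatment-end, identified as session 20 because 8.3.5 numbers that visit 21. Take it from the mixed model with categorical visit and group-by-visit terms, and report it with a confidence interval.
- State how V1 enters the model, and the alpha and sidedness. Bring the Protocol Summary's method into line.
- Make the omnibus interaction, the plot-guided trend models and the other instruments secondary, with no conclusion of overall effect drawn from them. Keep the interval effect sizes.
- State whether a claim needs both aims or either one. An adjustment such as Holm is needed only if either alone suffices.

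**Cost.** Wording in the Protocol Summary, 4.2.1, 10.2 and 10.4.2; no new data or patients. Some instruments become secondary. For a delayed effect the contrast gives up some power: about 77%, against 86% (omnibus) or 94% (trend) on reading (b). If either aim alone may support a claim, Holm's first step at 0.025 lowers adjusted power from 77–78% to 67–68%.
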